4 SAMPLE SIZE DETERMINATION

No formal sample size calculation has been performed. Only those subjects who have completed the previous study, XPF-009-301, are eligible to be enrolled into this study. Therefore, the expected total sample size will be up to approximately 40 subjects.

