7.7.5 Electrocardiograms

Observed and changes from OLE baseline of continuous ECG measurements will be summarized by treatment group and age groups (1 to 12 months and >12 to 84 months) at each scheduled visit. Additional summaries will be provided for ECG interpretation and will be summarized using frequency tables. Shift from baseline to post-baseline will also be provided for the ECG interpretation.

Potentially clinically significant abnormality categories listed below will be summarized using count and percentage.

Variable Name	Age group	Criterion
	NA	<= 300
QT interval corrected for heart rate by		>= 60 msec increase from
Fridericia's formula (QTcF) (msec)		baseline
		>= 500
OT Interval (msec)	NA	<= 300
QT Interval (msec)		>= 600
	1 to 12 months	>= 86 or $>=25%$ increase
OBS Interval (maga)		from baseline
QRS Interval (msec)	>12 to 84	>= 95 or $>= 25%$ increase
	months	from baseline
DP Internal (maga)	1 to 12 months	>= 141 or >= 25%
PR Interval (msec)		increase from baseline
	>12 to 84	>= 155 or $>= 25%$ increase
	months	from baseline
Haart rate (hpm)	1 to 12 months	>= 194
Heart rate (bpm)		<= 106
Haart rate (hpm)	>12 to 84	>= 123
Heart rate (bpm)	months	<= 62

Table 6: Potentially Clinically Significant ECG Abnormality Criteria

Listings will be provided for ECG data and potentially clinically significant abnormalities will be flagged in the listing.

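### The uncorrected QT limits in SAP Table 6 have no age band: in infants QT ≤300 msec mainly tracks heart rate, and QT ≥600 msec adds nothing to QTcF ≥500 msec

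*SAP*

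**What the plan says.** SAP section 7.7.5 plans two kinds of numerical ECG output. Continuous measurements, and their change from OLE baseline, are summarised by treatment group and by "age groups (1 to 12 months and >12 to 84 months) at each scheduled visit". Separately, "Potentially clinically significant abnormality categories listed below will be summarized" as counts and percentages, and the same abnormalities are flagged in the listing.

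The categories stand in Table 6:

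- **Uncorrected QT:** ≤300 or ≥600 msec, age group NA, with no reference to baseline.
- **QTcF** ("QT interval corrected for heart rate by" Fridericia's formula): ≤300 msec, ≥500 msec, or an increase of at least 60 msec from baseline, age group NA.
- **Heart rate:** flagged at ≤106 or ≥194 bpm for 1 to 12 months, and at ≤62 or ≥123 bpm for >12 to 84 months.
- **QRS and PR:** limits differ between the same two age bands.

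No reason is given for the QT limits. SAP section 2 and the protocol synopsis both list clinically significant ECG changes among the primary safety endpoints.

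**The concern.** Uncorrected QT shortens as heart rate rises, and the heart-rate rows of Table 6 accept much faster rates in infants than in older children. A single QT cut-off across both bands therefore means different things in each.

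The low cut-off is also the same number, 300 msec, for QT and for QTcF. The two measures coincide only at 60 bpm, where RR is one second, and that is below every heart rate the table leaves unflagged. At faster rates the QT row is the stricter of the two, so one ECG can be counted as abnormal on the QT row and pass on the QTcF row for no reason other than its rate. The high limit raises the opposite question: whether it can identify anything that the QTcF row does not.

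At stake is the readability of a safety table in a study whose primary objective is safety. With about 40 subjects, one flagged subject is 1/40 = 2.5% of the total.

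**Working it through.** There is no planned figure to reproduce. The limits are descriptive thresholds, and SAP section 4 says "No formal sample size calculation has been performed". The check applies the table's own correction to the table's own limits.

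**Inputs (all SAP Table 6):** QT limits 300 and 600 msec; QTcF limits 300 and 500 msec; heart-rate limits 106 and 194 bpm (infants), 62 and 123 bpm (older).

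**Formulas:** RR = 60 / heart rate, in seconds; QTcF = QT / RR^(1/3).

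| Heart rate (bpm) | RR (s) | RR^(1/3) | QTcF if QT = 300 | QTcF if QT = 600 |
|---|---|---|---|---|
| 106 (infant low limit) | 0.566 | 0.827 | 363 | 725 |
| 150 | 0.400 | 0.737 | 407 | 814 |
| 194 (infant high limit) | 0.309 | 0.676 | 444 | 887 |
| 62 (older low limit) | 0.968 | 0.989 | 303 | 607 |
| 100 | 0.600 | 0.843 | 356 | 711 |
| 123 (older high limit) | 0.488 | 0.787 | 381 | 762 |

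**Low limit, 1 to 12 months.** At a given rate, every QTcF at or below the fourth column gives QT ≤300.

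- At 150 bpm, QTcF 300 corresponds to QT 300 × 0.737 = 221 msec. A QT from 222 to 300 msec is therefore flagged on the QT row and not on the low QTcF row.
- For a fixed QTcF, the flag starts at heart rate 60 / (300/QTcF)^3. That is 104 bpm for QTcF 360 (so the whole unflagged infant range), about 122 bpm for 380, 142 for 400, 165 for 420 and 189 for 440. All these QTcF values lie inside the table's unflagged range of >300 to <500.

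**Low limit, >12 to 84 months.** The same mismatch exists but is smaller. Near 62 bpm the QT and QTcF rows almost agree (300 against 303), and they separate as the rate rises to 123 bpm.

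**High limit.**

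- In infants, RR at unflagged rates lies between 566 and 309 msec, so 600 msec is longer than the whole cardiac cycle throughout.
- In older children, RR lies between 968 and 488 msec, so 600 msec exceeds the cycle only above 60/0.600 = 100 bpm.
- In both bands, QT 600 gives QTcF 500 when RR = (600/500)^3 = 1.728 s, which is 60/1.728 = 34.7 bpm. At any faster rate, QT ≥600 already meets QTcF ≥500.
- Conversely, with QTcF below 500, QT at an unflagged rate stays below 500 × 0.827 = 414 msec (infants) or 500 × 0.989 = 495 msec (older).

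**Frequency of the low flag.** The documents give no QTcF distribution. As an illustration only, assume QTcF is normal with SD 20 msec and mean 380, 400 or 420. The share flagged is Φ((QTcF equivalent of QT 300 − mean)/20):

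- 150 bpm (equivalent 407): 91%, 64%, 26%
- 120 bpm (equivalent 378): 46%, 14%, 2%
- 100 bpm (equivalent 356): 11%, 1%, below 0.1%
- 80 bpm (equivalent 330): below 1% for all three means

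The spread is too wide to support any single figure.

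**The case against.** The strongest reply is that little depends on these rows. They feed counts and listing flags, with no test or decision rule. Table 6 is a screen for potential significance, whereas the endpoint concerns clinically significant change. QT and QTcF are different variables, so disagreement between them is not in itself a contradiction. The QTcF rows, the ECG interpretation tables with shifts, and the continuous summaries by age group all remain. The number of infants is not given, and a child who enters in the first year of life grows out of it within at most 12 of the 36 treatment months. All of this stands, and it limits the size of the point. It does not give the low-QT count a meaning in infants.

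A reader might infer more than the documents support:

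- **That 600 msec exceeds the cardiac cycle at all paediatric rates.** In the older band this is true only above 100 bpm. From 62 to 100 bpm the row is merely redundant.
- **That most normal infant ECGs would be flagged.** This needs an assumed QTcF distribution. The highest shares above are at 150 bpm, a rate that Table 6 itself flags as high in older children.
- **That a falling low-QT count over 36 months would be mistaken for a drug effect.** Section 7.7.5 does not say that the abnormality counts are tabulated by visit, whereas section 7.7.2 says so for liver abnormalities. The continuous summaries would also show a falling heart rate beside any QT change.

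**Conclusion.** The point holds in limited form. In the 1 to 12 month band, QT ≤300 msec counts ECGs that pass the table's own heart-rate and absolute QTcF limits, because the cut-off equates to a QTcF anywhere from 363 to 444 msec depending on rate. In the >12 to 84 month band the equivalent runs from 303 to 381 msec, so the distortion is smaller and the count is roughly interpretable at slower rates. QT ≥600 msec carries no information beyond QTcF ≥500 msec at any rate above about 35 bpm.

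These results need only Table 6 and Fridericia's formula. How many subjects would be affected cannot be computed from the documents. A reader might also infer that QT prolongation could be missed. It would not be, since the QTcF rows cover it. The consequence is a descriptive safety count that reflects heart rate more than repolarisation in infants. It is worth correcting because the correction is simple.

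**What to change.** Remove the two uncorrected QT rows from the Table 6 abnormality counts and the matching listing flags. Base QT-related counts on the QTcF rows already there (≤300 msec, ≥500 msec, increase of at least 60 msec). Keep uncorrected QT in the continuous summaries by age group and as a value in the listings.

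This needs a SAP wording change and two fewer table rows, with no new data and no new threshold. The downside is the loss of a low-QT count that has some meaning at slower rates in older children.

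If the sponsor prefers to keep the QT rows, it should reconcile them with the age-banded heart-rate rows and the QTcF rows of the same table and state the reason for the limits. The documents give no basis for proposing other QT limits, so none is suggested here.

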7.7.6 Other safety assessments

All neurological examination data will be listed using safety population.

Average daily diaper count per month and change in daily diaper counts per month from baseline will be summarized descriptively. Listings will also be provided. monthly average count is defined as (sum of daily diaper counts reported during the period, divided by the number of days within the time period when diaper count is reported) \times 28. Line plot will be provided for average daily diaper count (by monthly) by subject and treatment groups.

CCI	
CCI	results, sleep quality and palatability questionnaire values

will be listed.

7.8 Interim analysis

Safety data will be reviewed periodically through an independent data and safety monitoring board (DSMB) throughout the study.

Version: Final 1.0 Date: 04MAY2023 Page 40 of 47

[figure not shown]

tatistical Analysis Plan (SAP) 🛛 💥 🗶 E N O N

Appendix 1: Pediatric Quality of Life (PedsQL) Inventory scale score

DESCRIPTION OF THE QUESTIONNAIRE (INFANTS 1-12 MONTHS):

Dimensions	Number of Items	Cluster of Items	Reversed Scoring	Direction of Dimensions
Physical Functioning	6	1-6	1-6	
Physical Symptoms	10	1-10	1-10	
Emotional Functioning	12	1-12	1-12	Higher scores indicate better HRQOL.
Social Functioning	4	1-4	1-4	_
Cognitive Functioning	4	1-4	1-4	_

DESCRIPTION OF THE QUESTIONNAIRE (INFANTS 13-24 MONTHS):

Dimensions	Number of Items	Cluster of Items	Reversed Scoring	Direction of Dimensions
Physical Functioning	9	1-9	1-9	
Physical Symptoms	10	1-10	1-10	
Emotional Functioning	12	1-12	1-1 2	Higher scores indicate better HRQOL.
Social Functioning	5	1-5	1-5	_
Cognitive Functioning	9	1-9	1-9	_

SCORING OF DIMENSIONS:

Item Scaling	5-point Likert scale from 0 (Never) to 4 (Almost always)	
Weighting of Items	No	
Extension of the Scoring Scale	Scores are transformed on a scale from 0 to 100.	

Statistical Analysis Plan (SAP) 🛛 💥 🗶 E N O N

	Step 1: Transform Score
	Items are reversed scored and linearly transformed to a 0-100 scale as follows: 0=100, 1=75, 2=50, 3=25, 4=0.
	Step 2: Calculate Scores
	Score by Dimensions:
Scoring	 If more than 50% of the items in the scale are missing, the scale scores should not be computed.
Procedure	 Mean score = Sum of the items over the number of items answered.
	Psychosocial Health Summary Score = Sum of the items over the number of items answered in the Emotional, Social, and Cognitive Functioning Scales.
	Physical Health Summary Score = Sum of the items over the number of items answered in the Physical Functioning and Physical Symptoms Scales.
	Total Score: Sum of all the items over the number of items answered on all the Scales.
Interpretation and Analysis	If more than 50% of the items in the scale are missing, the Scale Scores should not be computed.
of Missing Data	If 50% or more items are completed: Impute the mean of the completed items in a scale.

DESCRIPTION OF THE QUESTIONNAIRE (Ages 2-4 year)

Dimensions	Number of Items	Cluster of Items	Reversed Scoring	Direction of Dimensions
Physical Functioning	8	1-8	1-8	
Emotional Functioning	5	1-5	1-5	Higher scores indicate
Social Functioning	5	1-5	1-5	better HRQOL.
School Functioning	3	1-3	1-3	

SCORING OF DIMENSIONS:

Item Scaling	5-point Likert scale from 0 (Never) to 4 (Almost always)				
Weighting of Items	No				
Extension of the Scoring Scale	Scores are transformed on a scale from 0 to 100.				
Scoring Procedure	Step 1: Transform Score				
	Items are reversed scored and linearly transformed to a 0-100 scale as follows: 0=100, 1=75, 2=50, 3=25, 4=0.				
	Step 2: Calculate Scores				
	 Score by Dimensions: If more than 50% of the items in the scale are missing, the scale scores should not be computed. Mean score = Sum of the items over the number of items answered. 				
	Psychosocial Health Summary Score = Sum of the items over the number of items answered in the Emotional, Social, and School Functioning Scales.				
	Physical Health Summary Score = Physical Functioning Scale Score				
	Total Score: Sum of all the items over the number of items answered on all the Scales.				
Interpretation and Analysis	If more than 50% of the items in the scale are missing, the Scale Scores should not be computed.				
of Missing Data	If 50% or more items are completed: Impute the mean of the completed items in a scale.				

DESCRIPTION OF THE QUESTIONNAIRE (Ages 5-7 year)

Dimensions	Number of Items	Cluster of Items	Reversed scoring	Direction of Dimensions	
Physical Functioning	8	1-8	1-8	N .	
Emotional Functioning	5	1-5	1-5	Higher scores indicate better HRQOL.	
Social Functioning	5	1-5	1-5		
School Functioning	5	1-5	1-5	_	

SCORING OF DIMENSIONS:

Item Scaling	5-point Likert scale from 0 (Never) to 4 (Almost always) 3-point scale: 0 (Not at all), 2 (Sometimes) and 4 (A lot) for the Young Child (ages 5-7) child report
Weighting of Items	No
Extension of the Scoring Scale	Scores are transformed on a scale from 0 to 100.
Scorin g Procedure	Step 1: Transform Score Items are reversed scored and linearly transformed to a 0-100 scale as follows: 0=100, 1=75, 2=50, 3=25, 4=0. Step 2: Calculate Scores Score by Dimensions: • If more than 50% of the items in the scale are missing, the scale scores should not be computed, • Mean score = Sum of the items over the number of items answered. Psychosocial Health Summary Score = Sum of the items over the number of items answered in the Emotional, Social, and School Functioning Scales. Physical Health Summary Score = Physical Functioning Scale Score Total Score: Sum of all the items over the number of items answered on all the scales.
Interpretation and Analysis of Missing Data	If more than 50% of the items in the scale are missing, the Scale Scores should not be computed. If 50% or more items are completed: Impute the mean of the completed items in a scale.

Note: Domain scores physical functioning, physical symptoms, emotional functioning, social functioning, cognitive and school functioning need to be derived according to the age group where applicable.

Appendix 2: Pediatric Quality of Life Inventory- Family Impact scale (PedsQL-FIM) DESCRIPTION OF THE FAMILY IMPACT MODULE:

Dimensions	Number of Items	Cluster of Items	Reversed Scoring	Direction of Dimensions
Physical Functioning	6	1-6	1-6	Higher scores indicate better functioning.
Emotional Functioning	5	1-5	1-5	
Social Functioning	4	1-4	1-4	
Cognitive Functioning	5	1-5	1-5	
Communication	3	1-3	1-3	
Worry	5	1-5	1-5	
Daily Activities	3	1-3	1-3	
Family Relationships	5	1-5	1-5	

SCORING OF DIMENSIONS:

Item Scaling	5-point Likert scale from 0 (Never) to 4 (Almost always)				
Weighting of Items	No				
Extension of the Scoring Scale	Scores are transformed to a 0 to 100 scale.				
Scoring Procedure	Step 1: Transform Score Items are reversed scored and linearly transformed to a 0-100 scale as follows: 0=100, 1=75, 2=50, 3=25, 4=0 Step 2: Calculate Scores by Dimensions • If more than 50% of the items in the scale are missing, the scale scores should not be computed, • Mean score = Sum of the items over the number of items answered. Step 3: Total Scores • The Total Score is the sum of all 36 items divided by the number of items answered • The Parent HRQL Summary Score (20 items) is computed as the sum of the items divided by the number of items answered in the Physical, Emotional, Social, and Cognitive Functioning scales. • The Family Functioning Summary Score (8 items) is computed as the sum of the items divided by the number of items answered in the Daily Activities and family Relationships scales.				
Interpretation and Analysis of Missing Data	If more than 50% of the items in the scale are missing, the Scale Scores should not be computed. If 50% or more items are completed: Impute the mean of the completed items in a scale.

1.1. Synopsis

Protocol Title:	An Open-label Extension Study of XEN496 in Pediatric Subjects With KCNQ2 Developmental and Epileptic Encephalopathy
Protocol Number:	XPF-009-302
Protocol Identifier:	EPIK OLE
Phase:	Phase 3
Study Drug:	XEN496: Immediate-release, multi-particulate sprinkle capsule formulation of ezogabine (retigabine) for pediatric subjects.
	Placebo: Matching capsules containing inactive ingredients (used only during the double-blind transition/titration period).
	The capsules are meant to be opened and the contents dispersed into soft foods or liquids for oral administration
Indication:	Treatment of seizures in pediatric subjects with KCNQ2 developmental and epileptic encephalopathy (KCNQ2-DEE).
Study Description:	An international, multicenter, open-label extension (OLE) study to assess the long-term safety, tolerability, and efficacy of XEN496 in pediatric subjects with KCNQ2-DEE who participated in the primary efficacy and safety study (XPF-009-301).
Objectives:	 Primary Objective: To assess the long-term safety and tolerability of XEN496 in pediatric subjects with KCNQ2-DEE who had participated in the primary study (XPF-009-301).
	Secondary Objectives:
	• To evaluate the intrasubject efficacy of XEN496 in reducing seizure frequency compared to prior placebo treatment in pediatric subjects with KCNQ2-DEE who were previously randomized to receive placebo in the primary double-blind Phase 3 study (XPF-009-301).
	• To assess the long-term effect of XEN496 on seizure reduction in pediatric subjects treated with XEN496.
	• To evaluate Caregiver Global Impression of Severity (CaGI-S) and Caregiver Global Impression of Change (CaGI-C) scores in pediatric subjects with KCNQ2-DEE.
	• To assess neurocognitive development and behavior after dosing with XEN496 in pediatric subjects with KCNQ2-DEE.
	• To evaluate the investigator's global impression of the change in the subject's overall condition, assessed using the Clinical Global Impression of Change (CGI-C) scale.
	• To evaluate the use of rescue medication and change in background antiseizure medications (ASM).

	• To assess the impact of XEN496 on the quality of life of caregivers and subjects with KCNQ2-DEE.
	• To evaluate the plasma concentrations of ezogabine and N -acetyl metabolite of retigabine (ezogabine) (NAMR).
Study Population:	Approximately 40 pediatric subjects diagnosed with KCNQ2-DEE who participated in the primary study (XPF-009-301).
Study Duration:	Subjects will undergo:
	• Screening/Baseline period – subjects will undergo eligibility assessment at Visit 22 or early termination in the primary study (XPF-009-301).
	• Treatment period – 36 months:
	\circ Blinded transition/titration period – 24 days.
	• Open-label period – approximately 35 months.
	• Taper period – Up to 15 days.
	Subjects who discontinue or complete the study treatment will be required to taper off study drug over a period of up to 15 days.
	• Follow-up – Approximately 4 weeks after subjects have tapered off study drug.
	Total study duration per subject is estimated to be 37 months.
Study Design:	Study Type: Interventional.
	Estimated Enrollment: Approximately 40 subjects.
	Intervention: Single group, open-label treatment with XEN496.
	Description: This is an open-label, long-term extension study of XEN496 for the treatment of seizures in subjects with KCNQ2-DEE, that will be open to eligible subjects who participated in the primary study, XPF-009-301. The primary objective is to assess the long-term safety of XEN496.
	The study includes a screening/baseline visit to assess eligibility. A double-blind transition/titration period will be used to maintain blinding to the treatment allocation in the primary study (XPF-009-301).
	After completion of the blinded transition/titration period, subjects will continue to receive the study drug at their optimal dose for approximately 35 months.
	Screening/Baseline:
	Screening/baseline procedures and assessments will be conducted at Visit 22 or early termination in the primary study (XPF-009-301); procedures and assessments in addition to those required at these visits may be conducted in order to confirm eligibility for the OLE study.
	Treatment Period:
	Blinded Transition/Titration Period:
	Subjects who received XEN496 in the primary study will continue to receive XEN496 at the same dose throughout the OLE.
	Subjects allocated to placebo in the primary study will be required to begin a titration of XEN496

	The transition/titration will be performed in a blinded manner to maintain the blind to the treatment arm from the primary study.
	Open-label Period:
	Following the transition/titration period, subjects will continue open-label treatment at their optimal dose of XEN496 for approximately 35 months.
	Taper Period and End of Study:
	At the end of the treatment period, subjects will be required to taper off study drug over a period of up to 15 days.
	Subjects who discontinue the study early will be required to enter into the taper period at that time and will be expected to complete the end of study follow-up safety monitoring schedule.
	Subjects will be monitored for safety for 28 days after the last dose of study drug has been administered.
Criteria for Subject	Criteria for Inclusion:
Selection:	To be eligible to participate in the study, an individual must meet all of the following criteria:
	 Subject completed participation as defined in the primary study, XPF-009-301. A subject who withdraws from the primary study due to meeting protocol-specified worsening criteria will be considered as having completed participation in the primary study.
	2. The caregiver is willing and able to comply with diary completion, visit schedule, and study drug administration requirements.
	3. Subject's caregiver achieved a minimum of 85% compliance with daily diary completion during both baseline and the double-blind period of the primary study.
	Criteria for Exclusion:
	Any subject who meets any of the following criteria will not qualify for entry into the study:
	 Any adverse event (AE) or serious adverse event (SAE) during Study XPF-009-301, which in the opinion of the investigator and sponsor's medical monitor, would preclude the subject's entry into the OLE.
	2. A clinically significant condition or illness, or symptoms other than those resulting from KCNQ2-DEE, present at screening/baseline that, in the opinion of the investigator, would pose risk to the subject if s/he were to enter the study.
	3. Any conditions that were specified as exclusion criteria in the primary study (XPF-009-301).
	4. It is anticipated that the subject will require treatment with at least one of the disallowed medications during the study.
	5.

Treatment Allocation:	All subjects rolling over into the OLE study will receive active treatment with XEN496. Subjects will undergo a blinded transition/titration period, regardless of their treatment allocation in the primary study (XPF-009-301).
Dosp Administration	Dose Administration:
